2.4.4. Demographics and Baseline Characteristics

Gender, race, and ethnicity will be summarized using counts and percentages. Age (years), height (cm), weight (kg), body surface area [BSA (m²)], Body Mass Index (BMI) (kg/m²) will be summarized with descriptive statistics.

The following baseline and pre-implant data recorded in the INTERMACS® database will be summarized:

- Patient demographic data.
- Medical history and co-morbidities.
- Clinical status including INTERMACS® patient profiles and NYHA Class.
- Laboratory values including blood chemistry and hematology.
- Cardiovascular Medications including inotropes, diuretics, anti-arrhythmics, pulmonary hypertensive agents, and anticoagulation therapy.
- Hemodynamic Data.
- Quality of Life as measured by EuroQol and KCCQ.
- Neurocognitive Testing measured by the Trail Making Neurocognitive Test, Part B.
- Exercise Function measured by the six minute walk test.

Continuous variables will be compared using the two-sided t-test, and the categorical variables will be compared using Fisher's Exact test. For the two sample t-test, the null hypothesis of equal variances among the groups will be checked. If the null hypothesis of equality of variance test is not rejected at the 0.05 level then the variances will be pooled, otherwise the Satterthwaite approximation for unequal variances will be used.

2.4.5. Patient Disposition

Disposition of Subjects

The number of subjects enrolled, who received an implant, and who are evaluable will be summarized. The number of treated subjects who completed the study, the number of subjects who discontinued from the study and the reasons for discontinuing from the study will also be summarized.

Protocol Deviations

Important protocol deviations (IPD) as defined by the HeartWare review team will be reported and presented with the final analysis.

2.4.6. Justification of Pooling

The primary and secondary endpoints will be performed on pooled data, however, an Analysis Site poolability assessment will be incorporated into the design of the study. This will involve pooling sites into “Analysis Sites” with a target size of 5 subjects. Sites with at least 5 subjects will serve at their own Analysis Site. Those with less than 5 will be rank ordered by size and sorted secondarily by site identification number to break ties. Starting with the smallest investigative site, subjects are combined site by site until at least 5 subjects are identified, thus establishing an Analysis Site. The next Analysis Site is formed similarly to contain at least 5 subjects. The process continues until all sites and subjects are accounted for. If the last Analysis Site has fewer than 5 subjects, it is combined with the most recently created previous Analysis Site.

A Fisher’s exact test will be performed to test the homogeneity of success at 6 months across Analysis Sites. Analysis Site homogeneity is defined if the p-value is 0.15 or greater. If there is an Analysis Site effect (p-value < 0.15), an investigation of prognostic factors (i.e., baseline characteristics, medical history or other covariates of interest) will be reviewed to understand variability between Analysis Sites. As a supplemental analysis, a logistic regression model will be performed to estimate the probability of success controlling for Analysis Site and the selected prognostic factors.

2.4.7. Additional Analyses

■ [REDACTED]

[REDACTED]

[REDACTED]

[REDACTED]

[REDACTED]

[REDACTED]

[REDACTED]

[REDACTED]

[REDACTED]

[REDACTED]

[REDACTED]

[REDACTED]

[REDACTED]

[REDACTED]

[REDACTED]

[REDACTED]

[REDACTED]

[REDACTED]

[REDACTED]

[REDACTED]

[REDACTED]

[REDACTED]

[REDACTED]

[REDACTED]

Adverse Events

i) Adverse Events based on INTERMACS definition

The number and percentage of subjects experiencing each specified AE using the INTERMACS definition will be summarized. Any AEs that are not treatment emergent will be listed only.

The incidence of AEs using the INTERMACS definition will be reported in the categories of bleeding (re-hospitalization, re-operation, gastrointestinal (GI)), cardiac arrhythmia (ventricular, supraventricular), device malfunction/failure, hemolysis, hepatic dysfunction, hypertension, infection (localized non-device, sepsis, driveline exit site), myocardial infarction, neurological dysfunction (CT confirmed ischemic cerebral vascular accident (CVA), CT confirmed hemorrhagic CVA , transient ischemic attack (TIA)), pericardial fluid collection, psychiatric

episode, renal dysfunction (acute, chronic), respiratory dysfunction, right heart failure (inotropic therapy, RVAD, inhaled nitric oxide), arterial non-CNS thromboembolism, venous thromboembolism, wound dehiscence, and other event. In addition to the incidence rate, the number of events and the event rate per patient year will be reported for each INTERMACS-defined adverse event. For the incidence rate, a subject will only be counted once per each INTERMACS-defined category and counted once per each INTERMACS-defined sub-category.

No statistical inference will be performed on adverse events.

2.5. Long-Term Follow-up Analyses

Adverse events through data cut will be included in the initial study results report. No other long term analysis will be included at that time. All data will be included in the final report.

2.5.1. Number and Timing of Proposed Analyses

Data collected post 6-months follow-up, i.e., 12, 18, and 24 months will be summarized and presented descriptively.

2.5.2. Endpoints

Analogue of the primary endpoint, as well as the secondary and other endpoints as possible will be included in post-6 months reporting.

2.6. Multivariate Analysis

No multivariate analysis is planned for this study.

3.1. Statistical Software

Version 9.4 or later of SAS® software will be the primary software used for statistical analysis.

3.2. Definition of Calculated Variables

1. Basic Variable Definitions

- Age will be calculated as the informed consent date minus the date of birth divided by 365.24 [Age=(ICF Date-DOB)/365.24]. Age will be rounded down to the nearest whole number
- Body mass index (BMI; kg/m²) is calculated as: weight (kg) / [height (m)]², rounded to one decimal place.
- Body surface area (BSA; m²) is calculated as:
$$BSA = (W * H / 3600)^{0.5}$$
where W = weight in kg and H = height in cm
- Weight will be displayed in kilograms (kg), height will be displayed in centimeters (cm), and temperature will be displayed in Celsius (C).
- Weights, heights, or temperatures recorded in alternate units will be converted to the units being displayed using standard conversion formulas.
- Length of Operative Time (Hours) = Time end of surgery for implantation – Time start of surgery for implantation
- Length of Initial Hospital Stay (Days) = Date of discharge following device implantation – date of hospitalization prior to device implantation + 1
- For days on or after the device is implanted:
Relative Study Day (Rel Day) = Date of Assessment – date of induction of anesthesia to implant of the study device + 1.
For days before the device is implanted:
Relative Study Day (Rel Day) = Date of Assessment – date of induction of anesthesia to implant of the study device.
- Days survived = Date of death/date of event for censoring – date of induction of anesthesia to implant of the study device + 1

- Days of hospitalization = Date of hospital discharge – Date of admission + 1
- Cumulative days of hospitalization after initial hospitalization is the sum of length of hospital stays after initial hospitalization.
- Days to first explant = Date of explant – date of induction of anesthesia to implant the initial study device + 1
- Days to first exchange = Date of exchange – date of induction of anesthesia to implant the initial study device + 1
- Days to transplant = Date of transplant – date of induction of anesthesia to implant the initial study device + 1
- Change from baseline (CFB) = Visit value – Screening/Pre-Implant value

2. Calculation of adverse event rate per patient-year

1. Calculate the patient-years contributed by each subject. The time in the study starts at enrollment. The end date would be the last follow-up date (end of study), unless the subject has an explant (when the pump is removed, turned off, or exchanged), dies, or is lost to follow-up prior to the end of study. The patient years are calculated as (date of explant or death or last follow-up or end of study – date of enrollment + 1)/365.24. When the number of days is negative, the value will be missing for the patient-years.
2. Sum the patient-years across all subjects in the study. This is the denominator.
3. Sum the total number of events for a particular adverse event (prior to exchange). If a subject has patient-years that is missing, the AEs will not be counted for these subjects (e.g., subjects who have ongoing AEs that are entered into the database, an exchange after the AE but prior to enrollment).
4. The adverse event rate per patient-year = (Sum of the total number of events for the particular adverse event (prior to exchange))/(Sum of the patient-years across all subjects in the study).

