1.2. Protocol Summary

This is a prospective, single arm, multicenter study to evaluate the safety and efficacy of the thoracotomy implant technique in 145 subjects implanted for the bridge to cardiac transplantation (BTT).

All subjects will be implanted via thoracotomy with the HeartWare Ventricular Assist Device (HVAD)® System and enrolled in the InterAgency Registry for Mechanically Assisted Circulatory Support (INTERMACS®) protocol and database.

This study will be conducted at up to 30 sites in the US and 1 site in Canada. All centers will be required to have an approved and active cardiac transplant program, have experience implanting the HeartWare® HVAD System, and must meet the INTERMACS® defined requirements to be eligible for participation.

One hundred forty-five (145) subjects will be required to meet the statistical endpoints defined for the study. It is anticipated that each site will enroll at least 1 subject. No site will implant more than 20 subjects into the study.

Subjects will be followed according to the INTERMACS® protocol and standard of care at the enrolling institution. Enrollment of subjects is expected to start in the fourth quarter of 2014 (First Implant) and each subject will be in the study for up to 60 months (including Screening and Follow-up phases).

The objective of this study is to evaluate the safety and effectiveness of implanting the HeartWare® HVAD System via thoracotomy in patients at risk of death from refractory end-stage left ventricular heart failure, who receive the device intended as a bridge to cardiac transplantation.

The primary endpoint is success at 6 months defined as all enrolled and implanted subjects:

- Alive on the originally implanted device at 6 months, and the subject has not had a stroke with a modified Rankin Scale ≥ 4 (assessed ≥ 3 months post stroke event); or
- Transplanted by Month 6, and the subject has not had a stroke with a modified Rankin Scale ≥ 4 (assessed ≥ 3 months post stroke event); or
- Explanted for recovery by Month 6, and the subject has not had a stroke with a modified Rankin Scale ≥ 4 (assessed ≥ 3 months post stroke event).

The secondary endpoint is an improvement in the mean length of initial hospital stay (initial recovery and step down unit) for all enrolled and implanted subjects. The mean length of initial hospital stay is estimated to be 26.1 days for median sternotomy subjects.

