2.1. Sample Size Estimate and Justification

2.1.1. Sample Size

Success at 6 months is estimated to be 86% compared to a performance goal of 77.5%. Using an exact binomial test, with a one-sided alpha of 0.05, and 80% Power, a sample size of 145 implanted subjects is required.

The target success estimate of 86% is based on the following:

- The primary endpoint observed in the final BTT IDE Report for the more recent BTT CAP population (N=242), resulted in a success rate of 85.8% (205 out of 239 eligible subjects) for sternotomy subjects.

- Post-approval data from the INTERMACS Registry (through Q2 2014), indicates similar results for the sternotomy population of 88.0% (396/450) with a lower rate of success for the small subset of thoracotomy (83.3%, 55/66) and thoracotomy on-pump (82.6%, 38/46) subjects.
- The INTERMACS Federal Partners Report (from Q1 2014) indicates an 85% Kaplan-Meier survival estimate at 6 months. This is not the same as “success” in that post-exchange survival is considered.

Success will be met if the lower bound of the upper one-sided exact 95% confidence interval is greater than 77.5%.

The mean length of initial hospital stay is estimated to be 26.1 days with a standard deviation of 22.8 days and a median of 20 days based on data from the BTT CAP population (N=242). Using a one sample t-test, with a one-sided alpha of 0.05, a sample of 145 implanted subjects with an average value of 21.3 days or less will result in power greater than 80%.

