2.4.2. Secondary Endpoint

The secondary endpoint is improvement in the length of initial hospital stay (initial recovery and step down unit) for all enrolled and implanted subjects, which is calculated by considering the number of days in acute care (ICU/CCU) plus the number of days in intermediate/step-down care (both variables taken as reported directly by INTERMACS), comprising the total number of days post-implant to discharge.

It is estimated that the mean length of initial hospital stay is 26.1 days for median sternotomy patients and thus the relevant hypotheses for this endpoint for each cohort are given by

$$H_0: \mu_T \geq 26.1$$

$$H_a: \mu_T < 26.1$$

where μ_T = the mean length of initial hospital stay for the Thoracotomy Implant Technique of the HVAD.

This secondary endpoint will be calculated and tested for each cohort using an upper tail one-sided t-test at 0.05 level of significance. Due to the skewed nature of this data, a one-sample sign test with an upper tail one-sided level of confidence of 0.05 will be conducted as supportive analysis.

The number and percentage of subjects with re-hospitalization after the initial hospitalization will be tabulated. Cumulative length of re-hospitalization after initial hospital stay (LOS) overall will be summarized using descriptive statistics, including 95% confidence intervals for the means.

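### The length-of-stay t-test names the wrong tail, and the tested stay is defined in two ways without a rule tying it to the 26.1-day benchmark

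*SAP*

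**What the plan says.** SAP 2.4.2 sets a null mean of at least 26.1 days against an alternative below 26.1. It then says that the endpoint will be "tested for each cohort using an upper tail one-sided t-test at 0.05 level of significance", with a supportive "one-sample sign test with an upper tail one-sided level of confidence of 0.05".

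The same section defines the stay as days in acute care (ICU/CCU) plus days in intermediate or step-down care, "both variables taken as reported directly by INTERMACS" and "comprising the total number of days post-implant to discharge".

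SAP 3.2, the list of calculated variables, gives the same name another content: "Length of Initial Hospital Stay (Days) = Date of discharge following device implantation – date of hospitalization prior to device implantation + 1". The list also has a separate general entry: "Days of hospitalization = Date of hospital discharge – Date of admission + 1".

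The benchmark appears in SAP 1.2: "The mean length of initial hospital stay is estimated to be 26.1 days for median sternotomy subjects". SAP 2.1.1 takes 26.1 days, SD 22.8 and median 20 from the CAP population (N=242) and states that "a sample of 145 implanted subjects with an average value of 21.3 days or less will result in power greater than 80" per cent, for a one-sample t-test at one-sided 0.05. Protocol 11.2 gives the same figures and describes the sign test as looking for a reduction from a median of 20 days.

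**The concern.** Two things in the SAP do not fit together.

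First, the named tail contradicts the hypotheses printed just above it. A program that followed the tail wording alone would look for longer stays and could not show the improvement that the endpoint is about.

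Second, the two definitions differ in start date (implant or an earlier admission), in data source (registry-reported unit days or calendar dates) and in counting convention (the added day). The SAP 3.2 entry cannot be set aside as a generic formula, because the generic one is listed separately. A programmer who looks up the endpoint by name in SAP 3.2 would build a different variable from the one in SAP 2.4.2.

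The definition matters more here than in a two-arm trial. There is no concurrent control in which a counting difference would cancel, and the planned effect is only 26.1 − 21.3 = 4.8 days. A stay counted on a different basis from the benchmark shifts the comparison by the full difference.

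**Working it through.** **Inputs.** Null mean 26.1, SD 22.8, n = 145, planned mean 21.3, one-sided alpha 0.05 (SAP 2.1.1, 2.4.2; Protocol 11.2). SE = 22.8/√145 = 1.893; df = 144; critical t = 1.6555.

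**1. Reproduce the stated power.** Noncentrality = (21.3 − 26.1)/1.893 = −2.535. Lower-tail power = P(T < −1.6555), with T noncentral t on 144 df, = 81.0%. This agrees with the stated figure of more than 80%. A two-sided 0.05 test would give 71.2%.

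**2. Compare the tails.**

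| | Lower tail (matches the hypotheses) | Upper tail (as worded) |
|---|---|---|
| Rejects when observed mean is | below 26.1 − 1.6555 × 1.893 = 22.97 | above 26.1 + 1.6555 × 1.893 = 29.23 |
| Probability of rejection at true mean 21.3 | 81.0% | about 0.0015% |
| p at observed mean 21.3 (t = −2.535) | 0.006 | 0.994 |

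The stated power can come only from the lower tail. At an observed mean of 21.3 the one-sided 95% upper confidence limit is 21.3 + 1.6555 × 1.893 = 24.4 days, below 26.1, which is the same decision as the lower-tail test.

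**3. Effect of a definition mismatch.** Let d be the mean number of extra days counted by the SAP 3.2 variable. The documents give no value for d, so the values below are assumptions; SD is held at 22.8 and the lower-tail test is used.

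- Case A: the benchmark and the planned 21.3 are post-implant figures, and the SAP 3.2 stay is tested. The tested mean is 21.3 + d and the noncentrality is (d − 4.8)/1.893.
- Case B: the benchmark includes pre-implant days, the SAP 2.4.2 stay is tested, and there is no true effect. The tested mean is 26.1 − d and the noncentrality is −d/1.893.

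| d (days) | 0 | 1 | 2 | 3 | 5 |
|---|---|---|---|---|---|
| Case A: power | 81% | 64% | 43% | 24% | 4% |
| Case B: false-positive rate | 5% | 13% | 28% | 47% | 84% |

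In Case A, power equals the 5% alpha level at d = 4.8, where the offset cancels the planned effect. The SD matters as well. In Case A with SD 20, power is 89% at d = 0 and 74, 51 and 29% at d = 1, 2 and 3. With SD 25 it is 74% at d = 0 and 57, 38 and 22%. So at SD 25 part of the shortfall is due to the SD and not to the definition.

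**4. Sign test.** If stays below 20 days are counted and there are no ties, the upper tail is the right direction: with Binomial(145, 0.5), P(X ≥ 83) = 0.048 and P(X ≥ 82) = 0.067, so the test rejects at 83 or more. It would be the wrong direction only if stays above 20 were counted. SAP 2.4.2 does not say which sign is counted.

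**The case against.** The tail wording is a drafting slip that the same section corrects. The printed hypotheses are as much a part of the rule as the tail label, the endpoint is called an improvement, and the protocol speaks of a reduction. Tail language is loose elsewhere too: SAP 2.1.1 describes the primary criterion by the lower bound of an upper one-sided interval. This stands. A reader might infer that the planned test cannot show a shorter stay, or that the sign test also runs the wrong way. The documents do not support either: the hypotheses settle the t-test's direction, and the sign-test wording is incomplete, not wrong.

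On the definition, SAP 2.4.2 is specific to the endpoint, and both SAP 1.2 and the Protocol's Study Summary describe the stay as initial recovery plus step-down unit alongside the 26.1-day figure. That makes SAP 2.4.2 the presumptive choice. It does not prove that the CAP days were counted that way, and no readable text says that it overrides SAP 3.2.

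The offsets are hypothetical, since no pre-implant stay is reported. A reader might infer that power has been lost. The documents do not show this; they show only that the test is sensitive to an offset of a few days, and that the error could equally favour the device.

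Finally, Protocol 11.1.3 shows no readable endpoint text and much of SAP 2.4.7 is redacted. Hidden text may state a precedence or use the SAP 3.2 variable. That limits the claim to what can be read, and it is a reason not to delete the SAP 3.2 entry.

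**Conclusion.** The point holds, in two parts of unequal weight. The t-test's tail is misnamed; this is certain but easily put right, because the hypotheses and the reproduced 81.0% power fix the intended direction. The double definition is the more consequential part, because nothing readable resolves it and the fixed comparator turns any counting mismatch into bias. The direction and size of that bias are unknown: they depend on how the CAP stays were counted and on the mean pre-implant stay, and neither is given. The ranges in the working are conditional on those assumptions and on SD 22.8.

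A reader might infer that adopting SAP 2.4.2 alone cures the problem. It does so only if CAP was counted on that basis. If CAP was counted from admission, SAP 2.4.2 would be the anti-conservative choice and a definition on the SAP 3.2 basis would remove the mismatch. Nor is the sample size in question: 145 subjects give the stated power on the stated inputs, and the primary analysis does not use this variable. This should be fixed before analysis.

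**What to change.** - **Tail.** In SAP 2.4.2, replace the upper-tail wording for the t-test with a lower-tail one-sided test at 0.05 or, equivalently, require the one-sided 95% upper confidence limit for the mean to be below 26.1 days.
- **Definition.** Before analysis, confirm how the CAP figures (26.1, 22.8 and 20 days) were counted: start date, units included and day convention. Then state one tested definition on that basis. SAP 2.4.2 is the presumptive choice. Rename the other variable and mark it descriptive. If the CAP basis cannot be established or matched, say so in the SAP and limit the conclusion drawn from the test.
- **Optional.** State that the sign test uses the protocol's null median of 20 days and rejects for an excess of stays below 20.

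The wording changes cost only an SAP revision. The effort of the CAP check cannot be judged from the documents, which do not say whether CAP recorded ICU and step-down days separately.

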2.2.2. Secondary Analysis Set

The Intent-to-Treat (ITT) population will include all enrolled subjects intended to receive the HVAD® pump via thoracotomy at the time of skin incision.

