2.4.3. Other Endpoints

Additional endpoints in this study include:

1. Success at 6 months defined as alive on original device or transplanted or explanted for recovery by month 6.
2. Overall Survival on HVAD (Time to Death on original device).

3. Frequency and rates of adverse events per INTERMACS® definition throughout original VAD support.
4. Time on Cardiac Pulmonary Bypass.
5. Perioperative Bleeding and Transfusions (within 48 hours post-op).
6. Length of initial ICU stay.
7. Prevalence and causes of re-hospitalizations (within 6 month period following implantation).
8. Health Status improvement at 6 month, as measured by KCCQ and EuroQol EQ-5D.
9. Functional status improvement, as measured by NYHA and 6-minute walk.
10. Success at 6 months (defined like the primary endpoint) for those screen failures who undergo thoracotomy.

Additional endpoints include observed and change in laboratory, hemodynamics and echocardiogram parameters and neurocognitive testing scores at 6 months. Additional observational endpoints will also be assessed at 6 months. The additional endpoints will be analyzed descriptively, i.e., no inferential analysis will be performed and conclusions will be formulated with caution as these endpoints are not powered.

Time-to-event outcomes will be presented using Kaplan-Meier curves. Quantitative outcomes will be summarized and the corresponding 95% confidence intervals will be derived.

Categorical outcomes will be summarized by presenting frequency and percentage results as well as the corresponding 95% confidence intervals. In particular, adverse events and stroke events summaries will be presented by calculating prevalence (frequency) and event rates (events per patient-year).

Strokes are neurological events specified as an ICVA or an HCVA, as per the current INTERMACS event definition (See Appendix D of the protocol).

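### SAP 3.2 starts adverse-event patient-years at an undated enrollment, although the endpoint covers time on the original VAD

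*SAP*

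**What the plan says.** SAP 3.2 item 2 computes each subject's patient-years from enrollment: "The time in the study starts at enrollment". The formula subtracts the enrollment date from the end date, adds 1 and divides by 365.24. The end date is explant (defined there to include removal, switching off or exchange of the pump), death, last follow-up or end of study.

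The item then adds an exclusion: "When the number of days is negative, the value will be missing for the patient-years". Events of subjects with missing patient-years are not counted. The example given is a subject with "an exchange after the AE but prior to enrollment".

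Two other places use a different time frame:

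- SAP 2.4.3 lists the endpoint as "Frequency and rates of adverse events per INTERMACS® definition throughout original VAD support".
- SAP 3.2 item 1 starts relative study day and days survived at the "date of induction of anesthesia to implant of the study device", and uses the equivalent date for days to first explant, first exchange and transplant. Not every interval in item 1 starts there: operative time starts with surgery, and the hospital-stay intervals start at hospitalization or admission.

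**The concern.** A rate per patient-year is interpretable only if numerator and denominator cover the same interval. Here the endpoint is time on the original device, but the denominator starts at an event that the readable text does not date. A programmer could take it as consent, registry enrollment, the day of surgery or a later registration date, and each choice gives a different rate from the same data.

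The exclusion adds a second problem. It can operate only if the end date, such as an exchange, can come before enrollment. In that case it removes subjects with early pump exchange together with their adverse events, and a device-safety summary should keep those subjects.

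Safety is a stated objective (SAP 1.3), and SAP 2.4.7 calls for an event rate per patient-year for every INTERMACS-defined event, so the rule feeds a whole set of safety tables.

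**Working it through.** **1. Is enrollment dated anywhere?** The passages that bear on it, side by side:

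- Protocol 9.1, headed Enrollment, names only the data source.
- Protocol 6.2.1 and 6.2.2 attach first and last implant to the start and end of enrollment, as calendar forecasts. This suggests enrollment at about implant.
- Protocol 11.1.1 and SAP 2.2.2 define the ITT set as "all enrolled subjects intended to receive the HVAD® pump via thoracotomy at the time of skin incision". This suggests enrollment by the time of surgery.
- Protocol 8.2 makes receipt of the device an inclusion criterion, and the INTERMACS protocol (Appendix A, A.1.1) includes patients who receive a device. Protocol 8.3 applies the study exclusions after registry enrollment. These leave enrollment after implant open.
- The example and the negative-days rule in SAP 3.2 item 2 have a function only if enrollment can follow implant.

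The text does not settle the order.

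**2. What did the sponsor's earlier rates use?** Protocol 4.2.1 gives 50 patients, mean support of 349 days and 47.8 patient-years. The check is 50 × 349/365.24 = 47.8, so that denominator is time on support. The SAP states no rate or gap of its own to reproduce.

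**3. Size of the error.** Let E be days of on-device exposure per subject, counted inclusively, and d the gap in days between enrollment and implant. Events are counted over VAD support from implant.

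- Enrollment before implant: the reported rate is E/(E + d) of the on-device rate, an understatement of d/(E + d).
- Enrollment after implant: the reported rate is E/(E − d) of the on-device rate, an overstatement of d/(E − d).
- d = 0: no error.

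The documents do not give d, so 7, 14 and 30 days are assumptions. E = 183 is 182 days plus 1, about six months. E = 349 is the mean support in Protocol 4.2.1. E = 913 is the 2.5-year maximum in Protocol 7.2, which is not a mean.

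| E (days) | d | Enrollment before implant: rate too low by | Enrollment after implant: rate too high by |
|---|---|---|---|
| 183 | 7 | 7/190 = 3.7% | 7/176 = 4.0% |
| 183 | 14 | 14/197 = 7.1% | 14/169 = 8.3% |
| 183 | 30 | 30/213 = 14.1% | 30/153 = 19.6% |
| 349 | 7 | 7/356 = 2.0% | 7/342 = 2.0% |
| 349 | 14 | 14/363 = 3.9% | 14/335 = 4.2% |
| 349 | 30 | 30/379 = 7.9% | 30/319 = 9.4% |
| 913 | 7 | 7/920 = 0.8% | 7/906 = 0.8% |
| 913 | 14 | 14/927 = 1.5% | 14/899 = 1.6% |
| 913 | 30 | 30/943 = 3.2% | 30/883 = 3.4% |

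The first block applies to a six-month summary. SAP 2.5 reports adverse events through data cut, where exposure is longer and the error smaller.

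**4. Example from the documents' own figures.** Protocol 4.2.1 reports 14 bleeding events over 22.3 patient-years in 50 patients for days 0-180: 14/22.3 = 0.63, as stated. A 14-day gap for each patient is 50 × 14/365.24 = 1.9 patient-years. Added to the denominator, this gives 14/24.2 = 0.58. Removed from it, this gives 14/20.4 = 0.69.

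**5. Events before a late enrollment.** The right-hand column assumes that these events stay in the numerator. If they were left out as well, the direction would depend on when each type of event tends to occur. In either case, subjects whose exchange precedes enrollment would lose both their time and their events.

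**The case against.** The strongest reply is that enrollment here simply means implant. Protocol 6.2 labels enrollment by first and last implant. SAP 1.2 allows up to 60 months in the study including screening, yet follows subjects to 5 years after implant; read literally, that leaves no pre-implant time. A definition could also sit in redacted text. The rates are descriptive, and SAP 2.4.7 rules out inference on adverse events. Defining the enrollment date would be enough.

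Much of this stands. A zero gap is possible, and the consequence is then nil. What does not stand is that the rule is harmless as written: the negative-days exclusion and its example have no function if enrollment equals implant. A definition would remove the ambiguity but would match the endpoint only if it named the implant date.

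A reader might go further and infer that the rates are biased low because consent comes before implant. The documents do not support that. Protocol 13.2 places consent before enrolling and before implant but does not order those two. SAP 2.4.5 plans that "The number of subjects enrolled, who received an implant, and who are evaluable will be summarized", but separate counts do not show separate dates. The 160 enrolled and 140 implanted in Protocol 4.2.3 belong to another trial, whose definition may differ. Nor can one infer the opposite, that enrollment follows implant, from one example in the SAP.

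**Conclusion.** The point holds as an undefined and mismatched time origin, with no established direction of bias. Any non-zero gap makes the stated rule give something other than the rate on the original device.

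Under assumed gaps of 7 to 30 days at 183 days of exposure, rates would be 3.7% to 14.1% too low if enrollment precedes implant. If it follows implant and events since implant are counted, they would be about 8% too high for 14 days. Both errors shrink as exposure lengthens, and both vanish if the dates coincide. These figures rest on gaps that the documents do not give.

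The matter is minor but worth correcting. It touches only the descriptive events per patient-year. Adverse-event percentages, the primary comparison with the 77.5% performance goal and the length-of-stay test are unaffected. The finding is limited to readable text: if a redacted passage equates enrollment with implant, the change below only makes that explicit.

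**What to change.** In SAP 3.2 item 2, compute patient-years as (the earliest of explant as that item defines it, death, last follow-up or end of study, minus the date of induction of anesthesia for the original implant, + 1)/365.24. The existing explant definition already covers exchange and removal at transplant, so no new end date is needed. State that events are counted over exactly the same interval.

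Delete the negative-days exclusion and its example, and query any negative value as a data error. No subject with an early exchange is then lost from the rates.

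The cost is a wording change in the SAP and one line of code. The anesthesia date is already required for the item 1 variables, so no new data are needed.
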